#### **SYNOPSIS** 1.

Name of Sponsor/Company: Adamas Pharmaceuticals, Inc.

Name of Investigational Product: ADS-5102 (amantadine HCl) Extended Release Capsules

Name of Active Ingredient: Amantadine hydrochloride

Title of Study: Open-Label Safety Study of ADS-5102 (amantadine HCl) Extended Release Capsules for the Treatment of Levodopa Induced Dyskinesia

**Study center(s):** Approximately 90 sites worldwide

**Study Duration:** Approximately 37 months (from enrollment of first subject to last subject completion [LSLV])

Phase of development: 3

### **Objectives:**

### **Primary:**

To evaluate the safety and tolerability of ADS-5102 oral capsules, an extended release formulation of amantadine, administered at a dose of 340 mg once nightly at bedtime for the treatment of levodopa induced dyskinesia (LID) in subjects with Parkinson's disease (PD).

### **Secondary:**

- To evaluate duration of ADS-5102 effect on dyskinesia as assessed by the Unified Parkinson's Disease Rating Scale (MDS-UPDRS), Part IV.
- To evaluate clinical progression of Parkinson's disease as assessed by MDS-UPDRS, Combined Score, Parts I, II, and III.

### **Study Design:**

This study will be offered to subjects who are described by one of the following 3 groups:

- Group 1 (current Adamas LID study subjects): Subjects who are participating in Adamas efficacy studies evaluating ADS-5102 in LID and choose to immediately transition into ADS-AMT-PD302 without a time gap;
- Group 2 (previous Adamas LID study subjects): Subjects who have previously participated in Adamas efficacy studies evaluating ADS-5102 in LID and will enter ADS-AMT-PD302 after a time gap;
- Group 3 (non Adamas LID study subjects with prior DBS): Subjects who would have been deemed ineligible for participation in previous or current Adamas efficacy studies due to having undergone deep brain stimulation.

Detailed inclusion/exclusion criteria and a schedule of events are described in this protocol Section 7 and Appendix A, respectively for each of these groups:

- Current Adamas LID study subjects (Group 1) should have their Screening Visit
  (Visit 1), including consent, for the ADS-AMT-PD302 study occur at the same
  visit as the final efficacy visit for the previous Adamas efficacy study, as outlined
  in the previous protocol. Subsequently, they should also have their Baseline Visit
  (Visit 2) for the ADS-AMT-PD302 study occur during the final study visit (not
  including any safety follow up visit) of the previous Adamas efficacy study visit,
  as outlined in the previous protocol.
- Previous Adamas LID study subjects (Group 2) and Non Adamas LID study subjects with prior DBS (Group 3) will not have overlapping visits with any previous protocol.

A study design schematic for study entry differences between these groups can be found in Appendix B.

Consented subjects who complete screening (Visit 1) and meet study eligibility criteria will have a baseline visit (Visit 2) and receive 1 week of 170 mg ADS-5102 (1 capsule) nightly at bedtime, followed by 340 mg ADS-5102 (2 capsules) nightly at bedtime for up to 99 additional weeks. The final week (Week 101) of dosing will be at the reduced dose of 170 mg ADS-5102 (1 capsule) nightly at bedtime.

Subjects will be enrolled into the study at Visit 2 (Week 0, Baseline) and return to the clinic after 4, 8, 16, 28, 40, 52, 64, 76, 88, and 100 weeks dosing. Subjects will receive a telephone reminder at the end of Week 1 to increase their dose to two capsules nightly at bedtime. At the Week 100 visit, subjects will be instructed to reduce their dose for 1 week, taking 1 capsule nightly at bedtime.

An efficacy assessment using the MDS-UPDRS will be completed at all study visits, beginning with the Screening Visit, with the exception of the Baseline/Week 0, Week 4, and Safety Follow Up visit. A safety follow-up visit will occur approximately 2 weeks following the completion of treatment. Women of childbearing potential will also have a pregnancy test performed at the early termination visit or 2 weeks following the completion of treatment at the final safety follow up visit.

Subjects who discontinue study drug before Week 101 will have an early termination visit that includes MDS-UPDRS assessments and safety follow-up.

Subjects who discontinue study drug after Week 4 should receive a reduced dose of 170 mg ADS-5102 for one additional week. The additional week of dosing at a reduced dose will not be needed for subjects who discontinue study drug before Week 4.

Adverse events (AEs) will be recorded beginning with the first dose of study drug and will continue through the safety follow-up visit. Concomitant medications will be recorded throughout the study.

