The underlying cause of LID is unknown, but the pulsatile administration of levodopa treatment and the degree of denervation in the striatum appear to influence its development (Del Sorbo et al., 2008). Other factors that have been associated with a higher incidence and severity of LID include early age of onset of PD, longer duration of levodopa treatment, levodopa total exposure, female gender, and genetic factors. The preferential use of dopamine agonists in the treatment of early disease and the careful management of pulsatile effects of levodopa therapy can delay but not eliminate the development of LID.

Amantadine IR, which is approved for the treatment of PD, is used off-label by movement disorder specialists and other neurologists to treat LID in patients with PD. A number of literature reports suggest amantadine is effective for the treatment of LID (Verhagen et al., 1998; Verhagen et al., 1999; Luginger et al., 2000; Snow et al., 2000; Paci et al. 2001; Thomas et al., 2004; da Silva-Junior et al., 2005; Sawada et al., 2010; Wolf et al., 2010; Goetz et al., 2013).

Despite amantadine's reported utility in the treatment of LID, until recently, the drug was not extensively studied in well-controlled clinical trials that meet evidence-based clinical or regulatory standards of acceptance, nor was the optimal dose for this indication established. The majority of patients with PD tolerate 200 mg/day of the amantadine IR formulation; however, the available literature on amantadine for the treatment of LID indicates that higher doses of amantadine produce a greater reduction in LID symptoms (Verhagen et al., 1998; Luginger et al., 2000). However, the increased frequency of adverse events (AEs) at higher doses, in particular central nervous system (CNS) events and sleep disturbances, limits the routine use of amantadine

Page 20 of 74

IR at doses of 300 mg/day or higher (Tyrrell et al., 1964; Jackson et al., 1967; Hayden et al., 1981).

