Subjects will be enrolled into the study at Visit 2 (Week 0, Baseline) and return to the clinic after 4, 8, 16, 28, 40, 52, 64, 76, 88 and 100weeks dosing. Subjects will receive a telephone reminder at the end of Week 1 to increase their dose during Week 2. At the Week 100 visit, subjects will be instructed to reduce their dose for 1 week, taking 1 capsule nightly at bedtime. The amount of available unused drug will be assessed during the Week 100 visit, and if a subject needs an additional bottle dispensed to cover 1 week of a reduced dose, they should be provided with a new bottle.

An efficacy assessment using the MDS-UPDRS will be completed at all study visits, beginning with the Screening Visit, with the exception of the Baseline/Week 0 visit & Week 4 visit. A safety follow-up visit will occur approximately 2 weeks following the completion of treatment. Women of childbearing potential will also have a pregnancy test performed at the early termination visit or 2 weeks following the completion of treatment at the safety follow up visit.

Subjects who discontinue study drug before Week 101 will have an early termination visit that includes MDS-UPDRS assessments and safety follow-up.

Subjects who discontinue study drug after Week 4 should receive a reduced dose of 170 mg ADS-5102 for one additional week. The additional week of dosing at a reduced dose will not be needed for subjects who discontinue study drug before Week 4.

Adverse events (AEs) will be recorded beginning with the first dose of study drug and will continue through the safety follow-up visit. Concomitant medications will be recorded throughout the study.

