#### 11.4. Week 4 +/- 1 Day (End of Week 4)

The following procedures will be performed:

- Assess and record concomitant medications;
- Assess and record Adverse Events;
- Targeted Physical Exam;
- Obtain subject weight in kilogram;
- Vital signs (blood pressure, respiratory rate, heart rate);
- Blood sample for central laboratory analysis including hematology, serum chemistry and eGFR;
- Urinalysis:
- Urine pregnancy test will be performed for all female subjects of childbearing potential;
- Collect unused study drug and bottles and evaluate compliance;
- Dispense study medication (4-week supply, 1 bottle of 60 capsules).

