### An AE **does not** include:

- medical or surgical procedures (e.g., surgery, endoscopy, tooth extraction, transfusion) Note: in this case, the condition that led to the procedure is an AE;
- pre-existing diseases or conditions present or detected prior to start of study drug administration, which do not worsen;
- the disease or disorder being studied or a sign or symptom associated with that disease (i.e., signs or symptoms associated with lack of efficacy will generally be considered to reflect underlying disease, rather than AEs):
- situations where an untoward medical occurrence has not occurred (e.g., hospitalization for elective surgery, social, and/or convenience admissions);
- overdose of either study drug or concomitant medication without any signs or symptoms. (Dosing details will be recorded on the appropriate eCRF(s)).

The Investigator should attempt to establish a diagnosis of the event based on the signs, symptoms and/or other clinical information. In such cases, the diagnosis should be documented as the AE (and SAE if serious) and not the individual signs/symptoms.

All AEs must be fully and completely documented on the AE page of the CRF and in the subject's medical notes. The following attributes must be assigned: description of AE, dates and times of onset and resolution (or whether ongoing), severity (Section 12.1.2), causality to study drug (Section 12.2), whether an SAE or not (Section 12.1.4), and action taken (i.e., no action taken; study medication interrupted; study medication discontinued; other).

Page 50 of 74

In the event that a subject is withdrawn from the study because of an AE, it must be recorded on the CRF. The subject should be followed and treated by the investigator until the AE has resolved or a new chronic baseline has been established

The investigator must report all directly observed AEs and all spontaneously reported AEs. At each visit the investigator will ask the subject a nonspecific question (e.g., "Have you noticed anything different since your last visit?") to assess whether any AEs have occurred since the last report or visit. AEs will be identified and documented on the AE page of the CRF in appropriate medical terminology.

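### The Week 1 telephone call is described only as a dose reminder, and the available text schedules no adverse event inquiry until Week 4, about three weeks into 340 mg

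*Protocol*

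**What the plan says.** Under the synopsis (Study Design), the first week is at one 170 mg capsule a night, and the step after it is described as "followed by 340 mg ADS-5102 (2 capsules) nightly at bedtime for up to 99 additional weeks". After Baseline subjects "return to the clinic after 4, 8, 16, 28, 40, 52, 64, 76, 88, and 100 weeks dosing", so Week 4 is the first clinic visit on drug.

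The call at the dose step is described twice. The synopsis wording is "Subjects will receive a telephone reminder at the end of Week 1 to increase their dose to two capsules nightly at bedtime". Section 6.1 has "Subjects will receive a telephone reminder at the end of Week 1 to increase their dose during Week 2". Each gives a single purpose.

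Section 11 sets out procedures contact by contact. Baseline (11.3) has no AE item, as expected before the first dose. The next entry is Week 4 (11.4), which contains "Assess and record Adverse Events". The call has no entry of its own. Section 12.1.1 says how AEs are actively sought: "At each visit the investigator will ask the subject a nonspecific question". It does not mention telephone contacts. Section 11 opens by referring to Appendix A for the schedule of evaluations.

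**The concern.** Safety and tolerability is the primary objective (Section 5.1). The Introduction says of immediate-release amantadine that "the increased frequency of adverse events (AEs) at higher doses, in particular central nervous system (CNS) events and sleep disturbances" limits its routine use at higher doses, and Section 4.1 adds that such effects can appear within hours of a dose. The extended-release product is meant to lessen this. Even so, Section 4.4 lists dizziness and hallucinations among the most frequent events in the earlier Phase 2/3 study. The first weeks of dosing are therefore a period in which good AE capture is worth having.

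Some subjects may be new to ADS-5102. Group 3 does not come from the efficacy studies, and those studies had placebo arms (SAP Section 3). The documents do not say how many such subjects will enter.

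What is at stake is completeness and dating. Section 12.1.1 requires onset dates and times on the CRF, and SAP Section 9.2.8 uses onset dates for Kaplan-Meier curves of neuropsychiatric events, falls and hallucinations. A mild event in Week 1 that the subject does not volunteer will first be asked about at Week 4. It may then be missed or only roughly dated.

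**Working it through.** The plan states no figure for this interval, so there is none to reproduce. The check is a comparison of sections plus day counts.

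**Inputs.** First dose at bedtime on Day 1, the day of the baseline visit (presumed in SAP Section 7.6). 170 mg for 7 nights, then 340 mg (synopsis; Table 3). Call at the end of Week 1. Week 4 visit at the end of Week 4, +/- 1 day (Section 11.4). One bottle of 60 capsules at Baseline (Section 11.3).

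1. *Nights at 340 mg before the first scheduled inquiry.* A daytime visit on Day d follows d - 1 nights of dosing, of which 7 were at 170 mg. Nights at 340 mg = d - 1 - 7.
   - Nominal visit on Day 28 or 29: 28 - 8 = 20, or 29 - 8 = 21.
   - With the +/- 1 day window, Day 27 to Day 30: 27 - 8 = 19, up to 30 - 8 = 22.
   - Roughly, 21 of the first 28 nights (21/28 = 75%) are at the higher dose.

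2. *Longest recall for an event on the first night.*
   - Asked at Week 4: 28 - 1 = 27 or 29 - 1 = 28 days, so about 28.
   - Asked at the call as well: about 7 days.
   - An event on night 8, just after the call, would still wait 28 - 8 = 20 or 29 - 8 = 21 days. The change therefore shortens recall for Week 1 events only.

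3. *Is any other contact scheduled at the step?* Capsules needed from Baseline to Week 4: 7 x 1 + 21 x 2 = 49, within the 60 supplied. No dispensing contact is needed, so the call is the only contact that the available text schedules in this interval.

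4. *Comparison with later intervals.* Gaps between clinic visits are 4, 4, 8, and then 12 weeks from Week 16 onwards. The first gap ties for the shortest in the study.

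5. *Which SAP curves are touched.* Under SAP Section 7.6, a subject who took 340 mg in an earlier study and enters without a gap keeps a baseline before that earlier first dose. If the onset clock follows the same rule, that subject's first weeks here are not the early part of the curve. The effect falls on subjects whose 340 mg clock starts in this study. Their number is not given.

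**The case against.** The strongest reply is that silence in two one-line descriptions does not show what the call covers. Section 11 defers to Appendix A, which may list AE review at Week 1. That stands: a reader might infer that the call asks nothing about AEs, but the available text shows only that no inquiry is described.

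A reader might also infer that the step to 340 mg is taken unchecked. The protocol does not support that. AEs are recorded from the first dose (synopsis; Section 6.1). Section 12 gives site personnel as well as the investigator the duty to query and record AEs during the study. Spontaneous reports must be recorded (12.1.1), so anything the subject mentions on the call counts. Emergency contact is arranged (16.5), and intolerable AEs are a listed reason to stop drug (7.5). Groups 1 and 2 exclude subjects who stopped earlier for AEs related to ADS-5102, and Groups 2 and 3 exclude documented amantadine intolerance. What remains is narrower: most of these safeguards need the subject to speak first, and none schedules a question before Week 4.

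A third inference is that events on 170 mg and on 340 mg become harder to tell apart. No planned summary makes that separation. The SAP Section 7.2 groups are placebo, 340 mg, 340 mg or more, and all ADS-5102.

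Finally, the first interval is no longer than any other, so recall there is already among the best in the study. That is fair. The case rests on the call already being made, not on the interval being unusually long.

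**Conclusion.** The point holds as a cheap improvement. On the available text, the Week 1 call is only a dose reminder, and the first scheduled AE inquiry follows 19 to 22 nights at 340 mg. For Week 1 events, maximum recall is about 28 days and could be about 7. The schedule applies to every enrolled subject (up to 250), although those with no earlier ADS-5102 exposure are an unknown part of that number.

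The analytic effect is limited to possible missed events and imprecise early onset dates in the SAP Section 9.2.8 curves. The documents give no basis for putting a size on that error. The AE recording window itself is sound.

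The conclusion assumes a first dose on the night of Day 1 and that Appendix A does not list AE review at the call. If Appendix A does list it, what is left is to align the body text with it.

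**What to change.** State whether AEs are asked about and recorded at the Week 1 call. Give the call its own entry in Section 11 as a documented contact, consistent with Appendix A and Sections 6.1 and 12.1.1. Staff would ask the nonspecific question already in Section 12.1.1, ask about concomitant medication, and record any AE with its onset date on the CRF. Extend Section 12.1.1 so that the question covers this contact as well as visits.

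The cost is a few minutes on a call already planned, a CRF entry where there is something to record, and amendment wording. No visit or procedure is added, and the dose schedule and stopping criteria stay as they are. The change does not shorten the wait for events that begin after the call; those still come up at Week 4.

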### **Methodology:**

The safety analysis population will include all enrolled subjects who receive at least one dose of study drug. Safety data will be summarized from the time of first dose and include all available safety data. No formal statistical testing will be done.

All AE data will be listed and will be summarized by system organ class, preferred term, and analysis group, as well as for all analysis groups combined. Quantitative safety variables (e.g., vital signs and clinical laboratory tests) will be summarized at each visit by analysis group, as well as for all analysis groups combined and changes from baseline will be summarized by analysis group at selected visits.

The efficacy analysis population will include all enrolled subjects who receive at least one dose of study drug and provide at least one post-enrollment MDS-UPDRS assessment.

MDS-UPDRS, Part IV and Combined Score, Parts I, II, and III data will be summarized across study visits and include all available data. The baseline MDS-UPDRS scores for a subject will be their MDS-UPDRS scores from the Screening Visit.

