### **Sample Size Justification:**

It is expected that a study size of up to 250 subjects and duration of treatment up to 101 weeks will support the goal of 100 subjects completing one year of treatment.

Number of subjects (planned): Up to 250

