### 7.3. Subject Withdrawal Criteria

Subjects will be advised that they are free to withdraw from the study at any time. Reasons that subjects may be withdrawn from the study include the following:

- Subject discontinued study medication (see Section 7.5);
- Subject consent is withdrawn;
- Sponsor decision, after discussion with the Investigator.

If a subject is withdrawn from the study, all efforts will be made to complete the early termination visit that includes efficacy assessments and safety follow-up. In addition, women of childbearing potential will have a pregnancy test performed at the early termination visit.

All information, including the reason for withdrawal, should be reported on the applicable pages of the case report form (CRF).

For subjects who are lost to follow-up, three documented attempts will be made to contact the subject for follow-up information, including reason for discontinuation and follow-up of AEs.

Subjects who withdraw from the study will not be replaced.

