### 13.1.4. Safety and Tolerability

The safety analysis population will include all enrolled subjects who receive at least one dose of study drug. Safety data will be summarized from the time of first dose and include all available safety data. No formal statistical testing will be done.

All AE data will be listed and will be summarized by system organ class, preferred term, and analysis group, as well as for all analysis groups combined. Quantitative safety variables (e.g., vital signs and clinical laboratory tests) will be summarized at each visit by analysis group, as well as for all analysis groups combined.

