9.2 Adverse Events

An adverse event (AE) is any untoward medical occurrence that occurs in conjunction with the use of a medicinal product in humans, whether or not considered to have a causal relationship to the medicinal product. An AE can, therefore, be any unfavorable or unintended sign (including a clinically significant abnormal laboratory finding), symptom, or disease

temporally associated with the use of a medicinal product, whether or not considered related to the medicinal product.

Adverse event data will be integrated, listed, and summarized for the Safety population. Events will be presented according to MedDRA® system organ class (SOC) and preferred term (PT). Summaries will be ordered alphabetically by SOC and PT, and by decreasing frequency of preferred term among all treatment/analysis groups regardless of whether a "total" column is presented.

Partial (Incomplete) AE onset and end dates will be listed as such. All AEs collected on the AE eCRF page will be considered treatment–emergent.

Most commonly reported (at least 2% of either active or placebo treatments) AEs will be presented by preferred term, and summarized by treatment/analysis group.

For each summary, at each of the SOC and PT levels, a subject will be counted once if he/she reported one or more AEs. Percentages will be calculated out of the number of subjects in the Safety population.

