9.2.8 Adverse Events of Special Interest

Adverse events of special interest are grouped into three event categories: Neuropsychiatric (CNS), Falls, and Hallucinations. The CNS category combines the following SOCs: Nervous system disorder and Psychiatric disorder. The Falls category combines all PTs that contain the term "Fall" or "Falls". The Hallucinations category combines all PTs that contain the term "Hallucination".

Event incidence will be summarized treatment/analysis group.

Time to onset will be analyzed and is defined as the number of days from the first dose of study drug to the onset of the first AE in the category. Subjects will be censored at the latest date known not to have had such AE. The median time to event and the associated 95% confidence interval for the Placebo and 340 mg ADS-5102 treatment groups will be estimated using the Kaplan-Meier method. Kaplan-Meier estimates of the survival function will be calculated and displayed graphically.

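### The PD302 protocol plans no adverse event analysis by time at risk; the integrated SAP supplies time to onset for three pooled categories only, so crude percentages will understate risk for events that arise throughout or late in treatment

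*Protocol*

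**What the plan says.** The primary objective of PD302 is safety and tolerability over up to 101 weeks of open-label treatment. The planned AE analysis, in the Synopsis under Methodology and again in 13.1.4, is: "All AE data will be listed and will be summarized by system organ class, preferred term, and analysis group", plus all groups combined. The sentence does not say whether subjects or events are counted, or over what time. Section 13.1.4 also says: "Safety data will be summarized from the time of first dose and include all available safety data". Vital signs and laboratory tests, by contrast, are to be summarised at each visit.

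On follow-up, the sample size statement is that up to 250 subjects "will support the goal of 100 subjects completing one year of treatment", and section 7.3 says: "Subjects who withdraw from the study will not be replaced".

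The supplied SAP is the Integrated Summary of Safety for AM201, PD301 and PD302. Its section 9.2 gives the only counting rule in the documents: "For each summary, at each of the SOC and PT levels, a subject will be counted once if he/she reported one or more AEs". The denominator follows: "Percentages will be calculated out of the number of subjects in the Safety population". SAP 9.1 summarises duration of exposure, but no AE table divides by it. SAP 9.2.8 does use time for three special-interest categories: "Time to onset will be analyzed and is defined as the number of days from the first dose of study drug". Its censoring rule is: "Subjects will be censored at the latest date known not to have had such AE". Those estimates are shown for pooled Placebo and pooled 340 mg, with subgroup repeats.

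**The concern.** A long open-label extension is the place to learn how often events occur over two years and whether new ones appear late. A subject who leaves event-free at Week 5 stays in the denominator with no further chance of contributing an event. (A subject with an event before leaving is counted correctly.) The crude percentage is therefore a mixture of risk and length of stay.

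Two misreadings follow. A reader who takes the printed percentage as the two-year risk will read it too low for events that keep arising. And because results are shown by analysis group, which I read as the three entry groups, groups with the same risk but different retention can look different. For SAEs, for AEs leading to discontinuation and for common AEs outside the three special-interest categories, no planned table shows when in treatment events begin.

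**Working it through.** **The plan's own figure.** The 250 and 100 come with no dropout rate or formula. Dividing gives 100/250 = 40% one-year retention. This cannot be checked further, since inflating 100 for 60% loss returns 250 only because the 60% comes from the same two numbers. As a target over a maximum, 40% is a floor and not a forecast, so I vary retention.

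**Inputs.** From the protocol: treatment up to 101 weeks, no replacement. Assumed: one-year retention R of 40%, 60% or 80%; constant dropout hazard, independent of event risk; true 101-week risk without dropout of 20%.

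**Constant event hazard.**
- Event hazard h = -ln(0.80)/101 = 0.00221 per week (11.5 per 100 subject-years).
- Dropout hazard d = -ln(R)/52 = 0.01762, 0.00982 or 0.00429 per week.
- Crude proportion = h/(h+d) × [1 - exp(-(h+d) × 101)].
- R = 40%: 0.1114 × 0.8650 = 9.6%.
- R = 60%: 0.1836 × 0.7034 = 12.9%.
- R = 80%: 0.3399 × 0.4814 = 16.4%.

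**All risk in weeks 0-8.** h = -ln(0.80)/8 = 0.02789; the same formula with 8 in place of 101.

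**All risk in weeks 52-101.** h = -ln(0.80)/49 = 0.00455; crude = R × h/(h+d) × [1 - exp(-(h+d) × 49)], where R is the share still present at Week 52.

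| One-year retention (assumed) | Mean weeks followed, of 101 | Crude, constant hazard | Crude, weeks 0-8 only | Crude, weeks 52-101 only |
|---|---|---|---|---|
| 40% | 47 | 9.6% | 18.7% | 5.4% |
| 60% | 64 | 12.9% | 19.3% | 9.6% |
| 80% | 82 | 16.4% | 19.7% | 14.5% |

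The true value is 20% in every cell. The ratio of crude to true is 0.48 to 0.82 at constant hazard, 0.94 to 0.98 for early events and 0.27 to 0.72 for late ones.

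**False group difference.** Two entry groups with the same 20% risk at constant hazard, one retaining 40% and the other 80% at one year, would print 9.6% and 16.4%. No group-specific retention is given, so this shows what can happen and does not predict it.

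**Why a single overall rate is not enough.** With all risk in weeks 0-8, one rate over the whole study would be 15.5 to 25.4 per 100 subject-years, against 145.5 in the first 8 weeks. The rate has to be given by interval.

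**The case against.** The strongest reply is that onset is not ignored. The integrated SAP plans censored Kaplan-Meier onset for three categories, one of which (Neuropsychiatric) is two whole organ classes and covers the CNS effects the protocol describes as the most commonly reported with immediate-release amantadine. These analyses are repeated by subgroup, including prior deep brain stimulation. The SAP also has event counts for these categories, start days in the AE listings, exposure duration, and Kaplan-Meier time to drug discontinuation. Section 4.1 of the protocol says CNS effects can appear within hours of dosing, and for early events the bias is negligible. Neither document calls the crude percentage a 101-week risk, and no testing is planned.

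Much of this stands. A reader might infer that PD302's AEs are summarised only as subjects with an event and that timing cannot be seen at all. The documents do not support that: the once-per-subject rule belongs to the pooled SAP, onset is analysed for three categories, and SAP 7.1 refers to individual study SAPs that were not supplied, so what the PD302 study SAP contains is unknown. A reader might also infer that crude figures will be about half the true risk. That ratio needs the 40% floor and a constant hazard together.

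The reply does not close the gap. The onset analysis pools 340 mg subjects across studies, is not shown by PD302 entry group, and is run on a PD302 database freeze. If the freeze fell on the SAP date of 13 November 2015 (my assumption), follow-up from the 14 July 2014 study start could not exceed about 70 weeks (487 days / 7). SAEs, AEs leading to discontinuation and other common AEs have no time-based summary in either document, and a listing is not an analysis.

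**Conclusion.** The concern holds for the protocol and the supplied SAP. Neither specifies an AE rate per subject-time, and time to onset is limited to three pooled categories. With independent dropout the crude percentage falls below the 101-week risk whenever that risk exceeds zero. The shortfall is small for events confined to the first 8 weeks (18.7% to 19.7% for a true 20%), material at constant hazard (about 10% to 16%), and largest for events after Week 52 (5.4% to 14.5%), which a study of this length is best placed to find. The sizes rest on assumed retention, independent dropout and stylised timing; the direction rests on independent dropout alone.

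One class needs separate treatment. For AEs leading to discontinuation, stopping for another reason is a competing event, so at final lock the crude percentage is close to the cumulative incidence, and what is missing there is mainly timing.

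This is a worthwhile and inexpensive improvement to a descriptive study. It does not invalidate the crude tables.

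**What to change.** In protocol 13.1.4 add for PD302, overall and by entry group where numbers allow:

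- First-event rates per 100 subject-years for common AEs, SAEs and AEs leading to discontinuation, by interval (0-8, 8-28, 28-52 and 52-100 weeks), using in each interval only subjects still at risk.
- Cumulative incidence with 95% CI at Weeks 28, 52 and 100. Use Kaplan-Meier for AEs and SAEs, with the independent-censoring assumption stated. Use the Aalen-Johansen estimator for AEs leading to discontinuation, with stopping for other reasons as the competing event.
- An explicit time origin. Group 1 subjects who roll over from active ADS-5102 without a gap may already have had up to 25 weeks of treatment in PD301, so PD302 Week 0 is not their first exposure. Show them separately from newly exposed subjects.
- A statement of whether subjects or events are counted in each table.

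Keep the crude tables. If the PD302 study SAP already contains these analyses, a cross-reference from 13.1.4 is enough.

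The cost is a few extra tables from AE onset dates and dosing dates already collected, with no new data and no hypothesis test. Some cells will be sparse, particularly late intervals within entry groups, and the reported long-term incidence will be higher than the crude percentages.
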